To calculate the sample size, we estimated that only 10% of participants in the placebo group will have a parasitemia below the microscopic limit of detection on day 7 versus 50% in the intervention group. With a power of 80% and an alpha error of 5% and considering a ratio 1:1 (treatment versus placebo group), we need 20 subjects in the placebo group and 20 subjects in intervention group. Accounting for a possible dropout rate of 10% in each study arm the final sample size will require recruitment of a total of 44 subjects.

Endpoints and assessment methods

Primary endpoint:

Parasitemia undetectable by thick blood smear on D7 after the start of administration of study drugs

Assessment method: Light microscopy

All those needing rescue treatment according to the physicians' judgement before day 7 will be counted as treatment failures together with all positives at day 7.

Secondary endpoints:

1) Parasitemia reduction $\geq 90\%$ on D7 compared with baseline assessed by light microscopy of thick blood smears

Assessment method: Light microscopy

2a) Time to parasitemia level < 100 parasites/ μl in the PZQ 3-day treatment group versus placebo assessed by microscopy

Assessment method: Light microscopy

2b) Time to parasitemia level below microscopic limit of detection in the PZQ 3-day treatment group versus placebo assessed by microscopy

Assessment method: Light microscopy

3) Occurrence of adverse events (AEs) in the PZQ 3-day treatment group versus placebo

Assessment method: Clinical examination and laboratory analysis

4) Time to parasite clearance assessed by qPCR in the PZQ 3-day treatment group versus placebo

Assessment method: Quantitative PCR

5) Parasitological cure rate assessed by qPCR on D7 after administration of study drugs

Assessment method: Quantitative PCR

6) Area under the curve (AUC) of microscopically-determined parasite mass between D0 and D7 in the PZQ 3-day treatment group versus placebo

Assessment method: Light microscopy

Exploratory endpoints

Proportion of participants with detectable gametocytes during D3-D7 in the treatment group versus placebo

Assessment method: Light microscopy

Duration of the study

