The subject may not enter the study if any of the following apply:

- Signs and symptoms of complicated malaria / severe malaria
- Taking an experimental drug in the last 4 weeks.
- Any antimalarial treatment in the last 4 weeks
- Is using and intends to continuing using a medication known to cause drug reactions with artemether/lumefantrine (e.g. cimetidine, metoclopramide, antacids, kaolin, terfenadine etc.)
- Use of systemic antibiotics with known antimalarial activity within 30 days of study enrolment (e.g. trimethoprim-sulfamethoxazole, doxycycline, tetracycline, clindamycin, erythromycin, fluoroquinolones, or azithromycin).
- Use of praziquantel within 30 days of study enrolment.
- Previous (within the last 10 years) participation in a malaria vaccine study
- Moderate to severe anemia (Hemoglobin level < 8 g/dL)
- Known history of hepatic disease or liver damage
- Any confirmed or suspected immunosuppressive or immunodeficient condition, including human immunodeficiency virus (HIV) infection
- Use of immunoglobulins or blood products within 3 months prior to enrolment
- Contraindications or known allergy to praziquantel or the first-line anti-malarial medication artemether/lumefantrine, or known or suspected allergy or intolerance to any other ingredient of the drug products (IMP/Non-IMP)
- Severe malnutrition (Body Mass Index (BMI) < 16.0)
- Pregnancy, lactation or intention to become pregnant during the study
- Known history of sickle cell anaemia, sickle cell trait, thalassemia or thalassemia trait
- Participants unable to be closely followed for social, geographic or psychological reasons
- Any other significant disease, disorder or finding which, in the opinion of the investigator, may significantly increase the risk to the participant because of participation in the study (e.g.

renal transplantation), affect the ability of the participant to participate in the study or impair interpretation of the study data.

Withdrawal of Participants

In accordance with the principles of the current revision of the Declaration of Helsinki (updated 2013) and any other applicable regulations, a participant has the right to withdraw from the study at any time and for any reason, and is not obliged to give his or her reasons for doing so. The Investigator may withdraw the participant at any time in the interests of the participant's health and well-being. In addition, the participant may withdraw/be withdrawn for any of the following reasons:

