- Administrative decision by the Investigator
- Ineligibility (either arising during the study or retrospectively, having been overlooked at screening)
- Significant protocol deviation
- Participant non-compliance with study requirements
- An AE, which requires discontinuation of the study involvement or results in inability to continue to comply with study procedures

The reason for withdrawal will be recorded in the case report form (CRF). If withdrawal is due to an AE, appropriate follow-up visits or medical care will be arranged, with the agreement of the participant, until the AE has resolved, stabilised or a non-trial related causality has been assigned. Any participant who is withdrawn from the study may be replaced, if that is possible within the specified time frame. The medical monitor may recommend withdrawal of participants. If a participant withdraws/is withdrawn from the study before reaching the criterion for malaria diagnosis, a complete, appropriate, curative course of anti-malarial therapy must be completed. The importance of this will be emphasised to study participants at screening. If a participant withdraws from the study, blood samples collected before their withdrawal from the trial will be used/ stored unless the participant specifically requests otherwise.

Pregnancy

Praziquantel is also considered safe for treatment of pregnant women (33). However, based on differential parasite kinetics between pregnant and non-pregnant participants, pregnant women should not be included in this current Phase II trial. Should a study participant become pregnant during the trial, she will be followed up as other participants and in addition will be followed until pregnancy outcome. We will not routinely perform nonessential venepuncture on such participants. All initial reports of pregnancy must be reported to the sponsor by the study-site personnel within 24 hours of their knowledge of the event using the appropriate pregnancy notification form. Abnormal pregnancy outcomes (e.g. spontaneous abortion, stillbirth, and congenital anomaly) are considered serious adverse events and must be reported using the Serious Adverse Event (SAE) Form. Any subject who becomes pregnant during the study must discontinue further study treatment and be withdrawn from the study. An antimalarial treatment will be administered to treat the *Plasmodium falciparum* infection according to national guidelines.

Treatment of trial participants

Allocation of the groups

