The procedures to be included in each visit are documented in Table 2. In General, during the treatment period (D0-D2) each visit is assigned a time point and a window period of ± 2 hours within which the visit will be conducted. Only the visits with study drug dosing time points (i.e. H0, H24, H48) are exempted from this and have a stricter window period of ± 1 hour. Between D3 and D7 the visit can be performed at any given timepoint on the respective day considering participant and study team convenience. Patients must be seen for all visits on the designated day within the given window period, or as close to it as possible. Missed or rescheduled visits should not lead to automatic discontinuation.

Screening visit

All potential participants will have a screening visit, which shall take place on the same day (i.e. within 24 hours) as the administration of study drugs. Informed consent will be obtained from those eligible as described above. Once the informed consent is signed, the following screening procedures indicated in Table 2 will be undertaken:

- Full medical history, clinical examination (including measurement of height and weight) and ascertainment of demographic details
- Vital signs (pulse, blood pressure and temperature);
- urine β -HCG test in female participants;
- Blood samples will be taken for full blood count, biochemistry, thick and thin blood smears, blood for RNA later.
- The inclusion and exclusion criteria for the study will be assessed

AEs will be recorded from the signature of the informed consent onwards. Abnormal clinical findings from the medical history, vital signs assessment or blood tests at any point in the study will be assessed using established reference intervals of CERMEL laboratory. If a laboratory test is out of range it may be repeated to ensure it is not a single occurrence. If an abnormal finding is deemed to be clinically significant, the participant will be informed and appropriate medical care arranged with the permission of the participant.

Study drug administration (D0-D2; H0, H24 and H48)

Medication will take place at CERMEL and participants will be hospitalized for 3 days. Before the medication is administered the following measures will be performed on all participant:

- Vital signs
- Thick and thin blood smears
- Blood in RNA later
- Potential adverse events (AEs)
- Potential concomitant medication is ascertained

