Definite	Clear-cut temporal association, with a positive re-challenge test or laboratory confirmation; Event or laboratory test abnormality, with plausible time relationship to drug intake; Cannot be explained by disease or other drugs; Response to withdrawal plausible (pharmacologically, pathologically) event definitive pharmacologically or phenomenologically (i.e. an objective and specific medical disorder or a recognized pharmacological phenomenon).
Probable	Clear-cut temporal association, with improvement upon drug withdrawal and not reasonably explained by the participant’s known clinical state. Event or laboratory test abnormality, with reasonable time relationship to drug intake. Unlikely to be attributed to disease or other drugs response to withdrawal clinically reasonable.
Possible	Event or laboratory test abnormality, with reasonable time relationship to drug intake. Less clear temporal association, other aetiologies are possible. Could also be explained by disease or other drugs, other possible aetiologies should be recorded on the Source Document Information on drug withdrawal may be lacking or unclear.
None	No temporal association with the study drug; related to other aetiologies such as concomitant medications or conditions or subject’s known clinical state. Event or laboratory test abnormality, with a time to drug intake that makes a relationship improbable (but not impossible) Disease or other drugs provide plausible explanations.

The investigator will document the **taken action(s)** following identification of the adverse event:

- No action taken
- Study drug discontinued
- Patient withdrawn from study
- Concomitant medication required

- Hospitalisation required or prolonged (this should also be reported as a SAE)
- Other

The investigator will follow-up the adverse event until resolution or until no further medically relevant information can be expected. **Adverse event outcome** will be classified as follows:

- Resolved
- Resolved with sequelae
- Continuing (at the end of the study)
- Death
- Unknown (if patient is lost-to-follow up and AE outcome is unknown)

Serious Adverse Event (SAE)

A SAE is an adverse event which:

- causes death or
- is life-threatening or
- necessitates or prolongs hospitalisation or
- results in persistent or significant disability/incapacity or
- is a congenital defect or malformation
- is another medically important event

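### The withdrawal list lets the investigator take a consenting participant out of the whole study, with no D7 smear, so an obtainable primary outcome can be lost; the expected effect is small

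*Protocol*

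**What the plan says.** All locations are in the protocol.

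- **Withdrawal of Participants.** The participant may leave at will, and the investigator may withdraw someone for health and well-being. Beyond that, "the participant may withdraw/be withdrawn for any of the following reasons": an administrative decision by the investigator, ineligibility arising or discovered late, a significant deviation, "Participant non-compliance with study requirements", or an adverse event that requires discontinuation or makes it impossible to keep to study procedures.
- **After withdrawal (same section).** The reason goes in the CRF. Follow-up is arranged only where an adverse event was the cause. "Any participant who is withdrawn from the study may be replaced". Samples already taken may be used. For a participant who leaves "before reaching the criterion for malaria diagnosis, a complete, appropriate, curative course of anti-malarial therapy must be completed". That diagnosis criterion is not defined in the text available.
- **Clinical visits.** "Missed or rescheduled visits should not lead to automatic discontinuation".
- **Actions taken after an adverse event (Causality assessment section).** "Study drug discontinued" is listed as a separate action from withdrawing the patient from the study.
- **Primary endpoint.** Participants needing rescue before day 7 "will be counted as treatment failures together with all positives at day 7". Withdrawal as such is not mentioned.
- **Sample size.** 10% clearance on placebo against 50% on praziquantel (PZQ), 80% power, 5% alpha, 20 per arm. "Accounting for a possible dropout rate of 10% in each study arm", the total is 44.

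**The concern.** The primary endpoint is one binary reading on one day in 22 people per arm. Four of the listed grounds (administrative, ineligibility, deviation, non-compliance) can apply to someone who still agrees to attend. The act that the list authorises is leaving the study, not stopping the drug, and nothing schedules a D7 smear afterwards. Replacement restores the head count but not the outcome of the person randomised.

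How a missing outcome is analysed can be left to a statistical analysis plan. Whether the smear is taken is fixed by the protocol. At stake is a modest loss of power if withdrawn participants are counted as failures, or some distortion if they are left out and the losses happen to be selective.

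**Working it through.** **1. Does any other text close the gap?**
- The Clinical visits sentence covers missed or rescheduled visits only; it does not limit the four grounds.
- The section on treatment of *P. falciparum* infection allows study treatment to be stopped with rescue, including on investigator judgment. That defines the outcome (failure) for those needing rescue, but not for someone withdrawn for a deviation or for administrative reasons.
- The adverse event actions show that stopping the drug is recognised as a separate, milder act. The withdrawal list does not use it.

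The gap remains.

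**2. The plan's own sample size.** Two-sided pooled two-proportion formula, no continuity correction, mean rate (0.10 + 0.50)/2 = 0.30:

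n = [1.96·√(2·0.30·0.70) + 0.8416·√(0.10·0.90 + 0.50·0.50)]² / 0.40² = (1.270 + 0.491)² / 0.16 = 19.4, rounded up to 20 per arm.

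20 × 1.10 = 22 per arm, 44 in total. The stated figures reproduce.

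**3. Method for the effect of withdrawals.** Exact binomial enumeration with 22 randomised per arm, Pearson chi-square without continuity correction, giving the probability of p < 0.05 in favour of PZQ. Placebo clearances are Bin(22, 0.10) unless stated. *Assumption:* one or two withdrawals on these grounds in the PZQ arm. Two equals the protocol's whole 10% allowance for that arm (22 − 20), so it is an upper illustration.

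**4. Counted as failures, 50% v 10%.** With k PZQ participants withdrawn regardless of outcome, PZQ clearances are Bin(22 − k, 0.50) out of 22.

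| Withdrawn | Power |
|---|---|
| none | 86.4% |
| one PZQ | 83.1% |
| two PZQ | 79.2% |
| two per arm | 82.2% |

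**5. Smears kept, 50% v 10%.** For two participants, PZQ clearances are Bin(20, 0.50) + Bin(2, q) out of 22, where q is the clearance rate of those who stopped the drug. For one participant, they are Bin(21, 0.50) + Bin(1, q).

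| q | Power, two kept | Gain over counting as failures |
|---|---|---|
| 10% | 80.73% | 80.73 − 79.20 = 1.5 points |
| 30% | 83.66% | 83.66 − 79.20 = 4.5 points |
| 50% | 86.40% | 86.40 − 79.20 = 7.2 points |

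For one participant the gain runs from 83.75 − 83.08 = 0.7 points (q = 10%) to 86.40 − 83.08 = 3.3 points (q = 50%).

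**6. Left out of the analysis.**

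| Lost | 30% v 10% | 50% v 10% |
|---|---|---|
| none | 39.3% | 86.4% |
| one PZQ non-clearer | 40.0% | not calculated |
| two PZQ non-clearers | 45.0% | 90.2% |
| two non-clearers per arm | 39.9% | 88.1% |
| two PZQ regardless of outcome | 36.8% | 84.1% |

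With no effect (10% in both arms), the chance of a false finding for PZQ is 2.16% with no loss and 2.26% with two PZQ non-clearers left out.

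**The case against.** **Little harm is shown.** The grounds are permissive. Participants are in hospital throughout dosing, a physician gives each dose, and follow-up lasts seven days, so such withdrawals should be few. The sample size already allows for two losses per arm: exact power at 20 v 20 is 83.8%, above the 80% target. This stands, and it is why the point is small.

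**A reader might infer bias towards PZQ.** One could note that 7/22 v 2/22 gives p = 0.062, while dropping two PZQ non-clearers gives 7/20 v 2/22 and p = 0.041. That example sits at the boundary and needs two losses, both on PZQ and both non-clearers. Losses unrelated to outcome move power the other way (39.3% to 36.8%), and the false-positive rate hardly moves. The documents give no reason to expect the selective pattern. Apart from the pharmacists and the administering physician, study physicians are blinded to allocation.

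**A reader might infer that PZQ side effects drive these losses.** Nausea, vomiting and abdominal pain are each listed at 10% or more. A dose refused for intolerance, however, falls largely under the separate adverse event ground, not the four discussed here. This objection is right, so a useful amendment must also reach adverse events that only stop dosing.

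**The remedy is not free.** If the curative course on withdrawal is given before D7, a later smear would reflect that drug. Keeping the smear meaningful means delaying that course. Some late-found ineligibility, such as recent antimalarial use, itself affects the D7 reading. Against leaving out two PZQ participants regardless of outcome (84.1%), keeping their smears at 10% clearance gives lower power (80.7%). All of this stands. The gain in power is relative to counting them as failures; the other benefit is an observed outcome for everyone randomised who still consents.

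**Conclusion.** The point holds as a cheap improvement to the protocol wording. An obtainable primary outcome can be given up at the investigator's discretion, and no analysis rule can restore it.

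The size is small, and nil if nobody is withdrawn this way. If withdrawn PZQ participants are counted as failures, one costs 3.3 points of power (86.4% to 83.1%) and two cost 7.2 (to 79.2%, just under target). If those who missed doses clear at about the placebo rate, keeping two smears recovers only about 1.5 points. The full 7.2 would require them to clear at 50% despite incomplete dosing.

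These figures rest on the protocol's planning rates, an uncorrected chi-square test, and one or two withdrawals on these grounds. The documents do not support reading this as inflated type I error, as a built-in advantage for PZQ, or as a rule that obliges withdrawal. No stated figure in the protocol is wrong on this point.

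**What to change.** Amend Withdrawal of Participants as follows.

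1. After the first dose, a protocol deviation, non-compliance, ineligibility without a safety concern, and an adverse event that only prevents further dosing end **study drug only**. Participants who still consent continue the scheduled smears to D7 under the existing rescue criteria, and rescue before D7 counts as failure under the existing endpoint rule.
2. Give the curative antimalarial course early only to those who actually leave the study or need rescue.
3. Remove the administrative ground after randomisation.
4. Keep withdrawal for withdrawn consent, health and well-being (including unsafe ineligibility), adverse events that require leaving the study, and pregnancy.

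**Cost.** One list and one clause change; the smears are already in Table 2. A few under-dosed or ineligible participants, some perhaps with recent antimalarial exposure, stay in the primary comparison, which may slightly dilute the observed effect. They wait until D7 for artemether/lumefantrine unless rescued.

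### The protocol lets randomised participants who are withdrawn be replaced, and the failure rule does not clearly classify them; the likely bias is small but can tip a borderline result

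*Protocol*

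**What the plan says.** Protocol, Withdrawal of Participants: "Any participant who is withdrawn from the study may be replaced, if that is possible within the specified time frame". The reasons listed just before it are an administrative decision, ineligibility found during the study or in retrospect, significant protocol deviation, non-compliance, and an adverse event that prevents continuation. The same section says that for someone who leaves before meeting the criterion for malaria diagnosis, "a complete, appropriate, curative course of anti-malarial therapy must be completed".

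Protocol, Sample size: "we estimated that only 10% of participants in the placebo group will have a parasitemia below the microscopic limit of detection". The time point is D7, and the PZQ arm is assumed to reach 50%. This gives 20 per arm. "Accounting for a possible dropout rate of 10% in each study arm", the total becomes 44, or 22 per arm.

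Protocol, Endpoints and assessment methods: those who need rescue treatment in the physicians' judgement "before day 7 will be counted as treatment failures together with all positives at day 7". Withdrawal and a missing D7 smear are not named.

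Protocol, Allocation of the groups: each eligible participant takes the next numbered sealed envelope. No separate rule is given for replacements. Protocol, Statistics: the primary comparison is a chi-square test, with no analysis population stated.

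**The concern.** Most of the listed reasons can arise after the envelope is opened and after dosing, and some may depend on treatment. Protocol, Potential risks for participants, lists nausea, vomiting and abdominal pain at 10% or more for PZQ. Withdrawal can be discretionary. The physician who gives the drug knows the allocation, and the two products are not identical.

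A rule that fills places in a fixed 22 per arm reads most naturally as substitution: one participant leaves the count and another enters it. The failure rule would protect against this if it clearly caught the person who left, but it does not. A curative course given because of withdrawal is not linked to rescue, and a withdrawn participant without a D7 smear is neither a rescue case nor a positive smear.

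If the people lost are mostly PZQ participants who would not have cleared, and they are replaced and not counted, the PZQ clearance rate is too high. Replacement also compensates for a loss that the sample size has already covered.

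**Working it through.** **Inputs.** From the Sample size section: clearance 10% on placebo and 50% on PZQ, 80% power, 5% alpha (taken as two-sided, since the protocol does not say), 1:1 allocation, 10% dropout. From the Statistics section: chi-square test, taken here without continuity correction. The numbers of participants replaced are assumptions.

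**1. The plan's own figure.** Pooled two-proportion formula, with mean rate 0.30:

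n = [1.960·√(2·0.30·0.70) + 0.842·√(0.10·0.90 + 0.50·0.50)]² / 0.40² = 19.4, so 20 per arm. Then 20 × 1.10 = 22 per arm, or 44 in total. The stated size reproduces, and the two extra places per arm are the dropout allowance.

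**2. No drug effect, protocol rate.** Both arms clear at 10%. Let the number of PZQ clearers be binomial(22, 0.10). Replace up to w of the PZQ non-clearers with new PZQ participants who clear with probability 0.10, and leave out those replaced. Nobody is replaced on placebo. Summing over all outcome pairs gives the chance of p ≤ 0.05 in favour of PZQ:

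| Replaced (w) | Expected PZQ rate | Chance of a significant result favouring PZQ |
|---|---|---|
| 0 | 2.2/22 = 10.0% | 2.2% |
| 2 | (2.2 + 0.2)/22 = 10.9% | 2.8% |
| 4 | (2.2 + 0.4)/22 = 11.8% | 3.6% |

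With four replaced, the figure is 5.8% if both arms clear at 30% and 9.8% if both clear at 50%. Those rates are three and five times the protocol's placebo assumption.

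**3. A borderline result.** Chi-square = N(ad − bc)² / (product of the four margins). Placebo is 2/22 throughout.

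- PZQ 8/22, replaced participants left out: 44·(8·20 − 14·2)² / (22·22·10·34) = 4.66, p = 0.031.
- Two replaced participants kept as failures, 8/24: 46·(8·20 − 16·2)² / (24·22·10·36) = 3.96, p = 0.046.
- Three kept as failures, 8/25: 47·(8·20 − 17·2)² / (25·22·10·37) = 3.67, p = 0.056.

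At the planned effect the conclusion does not move: 11/22 v 2/22 gives p = 0.003, and 11/26 v 2/22, with four kept as failures, gives p = 0.010.

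**4. Power without replacement.** Lost participants are scored as failures, 22 per arm, exact power of the chi-square test:

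- No loss, 50% v 10%: 86.4%.
- 10% lost in each arm, 0.9·50% = 45% v 0.9·10% = 9%: 81.1% (78.8% by the normal approximation).
- 10% lost in the PZQ arm only, 45% v 10%: 77.8%.

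**The case against.** A replacement sentence governs recruitment, not the analysis. Nothing in the protocol removes withdrawn participants from the denominator, and the analysis population may be set in a SAP that is not shown. This stands in part. A reader might infer that the randomised comparison is already lost, but the text only permits that outcome. An analysis set defined elsewhere would not, however, cancel the permission.

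Investigator judgement is a listed ground for rescue, so some withdrawals followed by curative treatment may count as failures. That is possible. The text leaves it open, and that ambiguity is the point.

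The adverse event percentages are incidences, not withdrawal rates. Dosing is in hospital, and follow-up ends at D7. Differential loss is therefore an assumption. If withdrawal is unrelated to clearance there is no bias under the null, and losing participants who would have cleared would lower the PZQ rate.

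A reader might also infer that replacement breaks the 1:1 blocks or requires someone to know the arm being refilled. The documents do not support this. The next numbered envelope continues the list, the replacement may fall in either arm, and replacement within an arm is not prescribed.

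**Conclusion.** The point holds as a defect in a stated rule. Replacement after randomisation is allowed for any reason, it duplicates the dropout allowance, and the failure rule leaves some of the people concerned unclassified.

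The size is modest. At the protocol's own 10% rate and about the planned loss (two of 22), the chance of a false result favouring PZQ rises by about 0.7 percentage points, and with four replaced by about 1.4. This assumes that everyone replaced is a PZQ non-clearer, that each replacement enters the PZQ arm, that none are replaced on placebo, and that the replaced are not analysed. A planned-size effect would survive. A borderline one might not: in the 8/22 example, three participants decide significance.

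It should not be inferred that power stays above 80% whatever happens once replacement is removed. That holds on exact calculation for 10% loss in both arms, but not for loss in the PZQ arm alone.

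**What to change.** Three changes of wording:

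- **Withdrawal of Participants:** limit replacement to participants withdrawn before the randomisation envelope is opened, so that no randomised participant is substituted.
- **Statistics:** state that all randomised participants are analysed in their allocated arm for the primary endpoint.
- **Primary endpoint:** as an analysis definition only, with no change to care, count as failure any antimalarial taken before the D7 smear for whatever reason, or a missing D7 smear after withdrawal. Scoring a missing smear as failure is one choice among several. What matters is that the choice is fixed before unblinding.

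The cost is a few sentences and no extra participants: the total stays at 44. Exact power is about 81% if 10% of each arm is lost and scored as failure, and about 78% if the 10% loss is in the PZQ arm only. The sponsor should accept that second figure knowingly.
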